Outcome of exploratory laparotomy (ex-lap) following war-related injuries has previously been extensively studied and reported on³⁻⁷. These reports have mainly concentrated on causes for and findings at ex-lap, and postoperative mortality (table 1). Few studies have focused on the differences in injury mechanism, complexity of injuries and outcome between civilians and combatants, especially in urban conflicts where IED's, human shields and suicide bombers are used².

Table 1. Findings at ex-lap and postoperative mortality in different conflicts

Conflict	Nb. of Ex-laps	Negative explorations	Small intestinal injuries	Colon injuries incl. rectum	Other injuries	Postoperative mortality
Chad,1980³	210	4,8%	33,0%	21,1%	32,7%	22,5%
Lebanon 1975-85⁴	1314	9,7%	24,7%	21,2%	55,0%	9,5%
Former Yugoslavia 1991-95⁵	93	4,3%	30,0%	28,4%	41,5%	10,8%
Gaza 2000-03⁶	230	6,5%	26,7%	17,9%	55,3%	7,4%
Mosul, Iraq, 2006⁷	153	15%	23,7%	18,7%	57,6%	33,3%

Justification

There is a need for better understanding of demographics and outcome of ex-lap following abdominal injuries sustained in urban conflicts where IEDs, human shields and suicide bombers are used. The use of these indiscriminate weapons could affect civilians to a greater extent than combatants⁸. We therefore hypothesize that the use of indiscriminate weapons in an urban setting causes more extensive abdominal injuries to the civilian population than to combatants. The knowledge gained from this study could be crucial when planning surgical staffing and facility needs in similar contexts.

Potential Risks and Benefits

Since this is an observational retrospective cohort study without any interventional methods it poses little to no harm for the participants. A potential benefit for future patients would be an increase in understanding among health care providers regarding what kind of abdominal injuries indiscriminate weapons cause. Furthermore, a better understanding of what impact the use of indiscriminate weapons has on the civilian population.

Aim of Study

To assess whether civilians have more complex abdominal injuries than combatants in an urban battle characterized by the use of indiscriminate weapons.

Primary Measure

Differences in injury mechanism, organs injured, surgical treatment given, postoperative complications and outcome between civilians *and* combatants.

Secondary Measures

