- Perioperative complication (Yes/No/Unknown, specified)
- Postoperative antibiotic prophylaxis (Yes/No/Unknown, specified)
- Postoperative infection (Yes/No/Unknown, appendix 3 for definition)
- Other postoperative complication (Yes/No/Unknown, appendix 2 for definition)
- Need of postoperative intensive care (Yes/No/Unknown, specified)
- Postoperative transfusions (Yes/No/Unknown, specified)
- Use of postoperative radiology (Yes/No/Unknown, specified)
- Further surgery done (Yes/No/Unknown, specified)
- Discharge (Yes/No/Unknown, specified)
- Follow-up scheduled (Yes/No/Unknown, specified)
- Re-admission (Yes/No/Unknown, specified)
- Deceased during hospital stay (Yes/No/Unknown, specified)
- Remarks

Statistical Analyses

Sample Size

Due to the nature of the study, the sample size will be a convenience sample of the available cases during the study period. It is expected that approximately 160 subjects will be enrolled.

Statistical Methods

Analysis will be done by as treated. A 5% significance level will be used. The difference in dichotomous, such as postoperative complication (primary outcome), and categorical outcomes with more than two categories will be tested using chi-square or Fisher test. For differences in continuous variables t-test will be used. In order to adjust our analysis for possible confounders and effect modifiers we will then use linear, logistic, ordinal or multinomial regression models, according to the nature of the outcome (continuous, binary, ordinal or nominal) with injury mechanism as the dependent variable and civilian/combatant as the main explanatory variable. Important demographic and injury specific parameters such as geographical location, date, age, sex, and injured organs, will then be included in the model as potential confounders.

Safety and Monitoring

Participant Confidentiality

The use of identification numbers will ensure anonymity in the data analysis. The participant's age, gender and demographic characteristics will be used as identifying features for analysis. The research team will ensure the ethical principles of beneficence, non-maleficence, justice and respect of patients are adhered to throughout the study.

Data Collection and Management

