Appendix 1: Penetrating Abdominal Trauma Index¹⁰

Overview

The Penetrating Abdominal Trauma Index (PATI) can be used to assess the severity of injury in patients with knife, gunshot or other penetrating wounds to the abdomen. The index can be used to compare performance of different emergency care settings.

Patient evaluation

1. 14 organs are examined
2. The risk associated with injury to each organ is graded from 1 to 5.
3. The estimated severity of each type of injury is graded from 1 to 5.

Organ Injured	Risk Factor	Injury	Injury Estimate
Duodenum	5	single wall	1
		≤ 25% wall	2
		>25% wall	3
		duodenal wall and blood supply	4
		pancreaticoduodenectomy	5
Pancreas	5	tangential	1
		through-and-through (duct intact)	2
		major debridement or distal duct injury	3
		proximal duct injury	4
		pancreaticoduodenectomy	5
Liver	4	nonbleeding peripheral	1
		bleeding, central or minor debridement	2
		major debridement or hepatic artery ligation	3
		lobectomy	4
		lobectomy with caval repair or extensive bilobar debridement	5
Large intestine	4	serosal	1
		single wall	2
		≤ 25% wall	3
		>25% wall	4
		colon wall and blood supply	5

Major vascular	4	≤ 25% wall	1
		>25% wall	2
		complete transection	3
		interposition grafting or bypass	4
		ligation	5
Spleen	3	nonbleeding	1
		cautery or haemostatic agent	2
		minor debridement or suturing	3
		partial resection	4
		splenectomy	5
Kidney	3	nonbleeding	1
		minor debridement or suturing	2
		major debridement	3
		pedicle or major calyceal	4
		nephrectomy	5
Extrahepatic biliary	2	contusion	1
		cholecystectomy	2
		≤ 25% common duct wall	3
		>25% common duct wall	4
		biliary enteric reconstruction	5
Small bowel	2	single wall	1
		through-and-through	2
		≤ 25% wall or 2-3 injuries	3
		>25% wall or 4-5 injuries	4
		wall and blood supply or >5 injuries	5
Stomach	2	single wall	1
		through-and-through	2
		minor debridement	3
		wedge resection	4
		>35% resection	5
Ureter	2	contusion	1

		laceration	2
		minor debridement	3
		segmental resection	4
		reconstruction	5
Bladder	1	single wall	1
		through-and-through	2
		debridement	3
		wedge resection	4
		reconstruction	5
Bone	1	periosteum	1
		cortex	2
		through-and-through	3
		intra-articular	4
		major bone loss	5
Minor vascular	1	nonbleeding small hematoma	1
		nonbleeding large hematoma	2
		suturing	3
		ligation of isolated vessels	4
		ligation of named vessels	5

where:

- The percent injury to an organ wall probably indicates the portion of the entire circumference involved.

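### If the adjusted regression is applied to in-hospital death, the roughly 12 to 53 deaths expected are few for the covariates listed, and the plan has no coding or sparse-data method

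*Combined protocol and SAP*

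**What the plan says.** **Sample size.** The Sample Size section says that "the sample size will be a convenience sample of the available cases during the study period" and then: "It is expected that approximately 160 subjects will be enrolled". It gives no expected number of deaths.

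**Outcomes.** Primary Measure and Secondary Measures list outcome among the comparisons. Data Sources spells out that outcome includes death, and Patient Files records death during the hospital stay. Statistical Methods labels postoperative complication as the primary outcome.

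**Adjusted analysis.** Statistical Methods provides for "linear, logistic, ordinal or multinomial regression models, according to the nature of the outcome (continuous, binary, ordinal or nominal"). The same sentence continues "with injury mechanism as the dependent variable and civilian/combatant as the main explanatory variable". It then gives a list, introduced as examples, under which "geographical location, date, age, sex, and injured organs, will then be included in the model as potential confounders".

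**What is left open.** The plan does not say how location, date or injured organs are coded, how many terms may enter, or what happens if a model does not converge. Patient Files records location as an open field. Fisher's test is allowed for unadjusted comparisons, but the adjusted models have no counterpart for sparse data.

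**Mortality figures.** The only rates in the document are in the "postoperative mortality" column of Table 1, for five earlier series.

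**The concern.** In logistic regression, the information is limited by the rarer outcome, here the deaths. With many covariates and few deaths, two things go wrong. The model fits noise, so its coefficients are too extreme for new data. And some combination of covariates may predict death or survival perfectly (separation), in which case at least one maximum-likelihood estimate is infinite.

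The adjusted mortality comparison of civilians with combatants is at stake. It could come out imprecise or inflated. With no coding fixed in advance, the covariates might also be settled after seeing which models converge.

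**Working it through.** **1. Expected deaths.** The plan states none, so there is no figure to reproduce. Deaths = 160 × Table 1 mortality.

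| Table 1 series | Mortality | Deaths in 160 |
|---|---|---|
| Gaza 2000-03 | 7.4% | 11.8 |
| Lebanon 1975-85 | 9.5% | 15.2 |
| Former Yugoslavia 1991-95 | 10.8% | 17.3 |
| Chad 1980 | 22.5% | 36.0 |
| Mosul 2006 | 33.3% | 53.3 |

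Weighted by number of laparotomies, the rate is (210×0.225 + 1314×0.095 + 93×0.108 + 230×0.074 + 153×0.333) / 2000 = 250.1/2000 = 12.5%, or about 20 deaths.

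**2. Deaths per term.** Three codings are compatible with the text. All contain civilian status, sex, age and linear date.

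| Coding (intercept not counted) | Terms | At 11.8 deaths | At 53.3 deaths |
|---|---|---|---|
| Binary location, organ count | 6 | 2.0 | 8.9 |
| Location in 4 groups, 5 organ indicators | 12 | 1.0 | 4.4 |
| Location in 5 groups, 14 organ indicators | 22 | 0.5 | 2.4 |

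Example: 11.8/22 = 0.54 and 53.3/22 = 2.42. With location in 4 groups and 14 indicators (21 terms), the figures are 0.56 and 2.54.

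**3. Separation.** Datasets of 160 were simulated, 300 to 400 per cell, and checked for separation by linear programming. Assumed, not in the documents: 15% women, the age distribution, location shares, organ prevalences, and a weaker and a stronger set of effects. Civilian status was derived from age and sex as in the List of Definitions, which made 38% civilian. Ranges cover the two effect sets.

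| Terms | 12 deaths | 20 deaths | 36 deaths | 53 deaths |
|---|---|---|---|---|
| 6 | 12-18% | 3-4% | 0% | 0% |
| 12 | 57-61% | 22-28% | 5-6% | 2-3% |
| 22 | 96-99% | 88-93% | 54-64% | 38-39% |

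**4. Overfitting.** Median calibration slope in new data, from fits without separation (1 means no overfitting): 0.33-0.76 with 6 terms, 0.18-0.52 with 12, and 0.14-0.45 with 22. The 22-term values at the lowest mortality rest on very few fits, because nearly all datasets separated.

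**5. The civilian odds ratio.** True value 2, stronger effects, fits without separation; median and central 95% of estimates:

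| Terms | 12 deaths | 36 deaths | 53 deaths |
|---|---|---|---|
| 6 | 1.90 (0.23-9.5) | 1.95 (0.70-6.46) | 2.00 (0.82-5.31) |
| 12 | 2.57 (0.22-13.2) | 2.11 (0.50-5.56) | 1.97 (0.65-5.65) |
| 22 | 2.67 (0.48-14.0; 12 fits) | 2.47 (0.59-9.54) | 2.27 (0.74-6.26) |

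Under the weaker effects, the median standard error of the civilian log odds ratio with 6 versus 22 terms was 0.50 versus 0.56 at 36 deaths and 0.45 versus 0.50 at 53.

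**6. Does penalisation help?** In a further simulation, also on assumed prevalences and effects, Firth penalisation with the same covariates lowered the root mean squared error of the civilian log odds ratio in every cell. At 7.4% mortality it fell from 1.73 to 0.98 with 22 terms and from 0.98 to 0.85 with 6.

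**The case against.** **The plan does not write out a model for death.** Its regression sentence names injury mechanism as the dependent variable, and the labelled primary outcome is postoperative complication, for which no rate is given. A reader might infer that a mortality model with the full covariate list is explicitly planned. The text does not say so, and the point must be conditional. The condition is nonetheless a natural reading. Linear, ordinal and binary models would have no use if the only dependent variable were injury mechanism, which Patient Files records as a nominal variable with many categories.

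**Fourteen organ indicators are an assumption.** The statement "14 organs are examined" describes how the Penetrating Abdominal Trauma Index (PATI) is scored, and PATI is a single sum. Table 1 groups injuries into three. A reader might infer that logistic regression will usually separate. The documents do not fix a coding that would make this so: with six terms separation is 18% or less, and with twelve it is rare at 36 to 53 deaths. This objection stands. What remains is that the plan does not exclude the unfavourable coding.

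**A diverging nuisance coefficient need not spoil the main contrast.** A reader might infer that the adjusted mortality result would be unusable. That is too strong. In the simulation of step 6, some coefficient diverged in 98% to 18% of 22-term fits from the lowest to the highest mortality, but the civilian coefficient did so in at most 6%. A separate 21-term simulation gave 8-9% for the civilian coefficient at 7.4% mortality and 0% at 12.5% and above. At 36 deaths or more, the loss of precision in step 5 is modest.

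**The mortality rates are borrowed.** The Background says that the hospital mainly received referrals after late December 2016, so deaths could fall outside 12 to 53. This also stands.

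**Conclusion.** The concern holds in conditional form. If the general regression sentence is applied to in-hospital death, 160 patients at Table 1 rates give about 12 to 53 deaths: roughly 2 to 9 per term with lean coding, and about 0.5 to 2.5 with 14 organ indicators. Ordinary logistic regression is then likely to overfit whatever the coding. It will often separate if organs are entered individually and deaths are few. The civilian odds ratio loses precision and, with many terms and few deaths, tends to be inflated.

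The counts and ratios are arithmetic on the protocol's own numbers. The separation rates, slopes and odds-ratio ranges depend on assumed covariate distributions and effects and are indicative only. Much of the width at 12 deaths comes from the small number of deaths, and no choice of method removes it: even six terms gave 0.23 to 9.5.

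**What to change.** Amend Statistical Methods as follows:

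1. State which outcomes are modelled with adjustment, and reconcile this with the clause that makes injury mechanism the dependent variable.
2. For death and other sparse binary outcomes, named in advance, fit Firth-penalised logistic regression with profile-likelihood intervals.
3. In these models, enter organ injury as one pre-specified summary term, such as the PATI total or the number of injured organs, or leave it out. Do not use 14 indicators. Fix the coding of location and date before the analysis.
4. Report the unadjusted risk difference with its confidence interval beside the adjusted odds ratio. The planned chi-square or Fisher test gives a p-value but no effect size.

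The documents supply no basis for a particular event threshold or a fixed maximum number of terms, so the amendment need not adopt either. As deaths become more numerous, Firth estimates approach the ordinary ones, so little is lost if the outcome proves less sparse than feared.

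The cost is a few sentences of SAP text and standard software; no new data are needed. The downside is slightly less detailed adjustment for organ injury.

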Appendix 1: Penetrating Abdominal Trauma Index¹⁰

Overview

The Penetrating Abdominal Trauma Index (PATI) can be used to assess the severity of injury in patients with knife, gunshot or other penetrating wounds to the abdomen. The index can be used to compare performance of different emergency care settings.

Patient evaluation

1. 14 organs are examined
2. The risk associated with injury to each organ is graded from 1 to 5.
3. The estimated severity of each type of injury is graded from 1 to 5.

Organ Injured	Risk Factor	Injury	Injury Estimate
Duodenum	5	single wall	1
		≤ 25% wall	2
		>25% wall	3
		duodenal wall and blood supply	4
		pancreaticoduodenectomy	5
Pancreas	5	tangential	1
		through-and-through (duct intact)	2
		major debridement or distal duct injury	3
		proximal duct injury	4
		pancreaticoduodenectomy	5
Liver	4	nonbleeding peripheral	1
		bleeding, central or minor debridement	2
		major debridement or hepatic artery ligation	3
		lobectomy	4
		lobectomy with caval repair or extensive bilobar debridement	5
Large intestine	4	serosal	1
		single wall	2
		≤ 25% wall	3
		>25% wall	4
		colon wall and blood supply	5

Major vascular	4	≤ 25% wall	1
		>25% wall	2
		complete transection	3
		interposition grafting or bypass	4
		ligation	5
Spleen	3	nonbleeding	1
		cautery or haemostatic agent	2
		minor debridement or suturing	3
		partial resection	4
		splenectomy	5
Kidney	3	nonbleeding	1
		minor debridement or suturing	2
		major debridement	3
		pedicle or major calyceal	4
		nephrectomy	5
Extrahepatic biliary	2	contusion	1
		cholecystectomy	2
		≤ 25% common duct wall	3
		>25% common duct wall	4
		biliary enteric reconstruction	5
Small bowel	2	single wall	1
		through-and-through	2
		≤ 25% wall or 2-3 injuries	3
		>25% wall or 4-5 injuries	4
		wall and blood supply or >5 injuries	5
Stomach	2	single wall	1
		through-and-through	2
		minor debridement	3
		wedge resection	4
		>35% resection	5
Ureter	2	contusion	1

		laceration	2
		minor debridement	3
		segmental resection	4
		reconstruction	5
Bladder	1	single wall	1
		through-and-through	2
		debridement	3
		wedge resection	4
		reconstruction	5
Bone	1	periosteum	1
		cortex	2
		through-and-through	3
		intra-articular	4
		major bone loss	5
Minor vascular	1	nonbleeding small hematoma	1
		nonbleeding large hematoma	2
		suturing	3
		ligation of isolated vessels	4
		ligation of named vessels	5

where:

- The percent injury to an organ wall probably indicates the portion of the entire circumference involved.

organ score = (risk factor) × (injury estimate)

penetrating abdominal trauma index (PATI) = SUM (all injured organs)

Interpretation

- minimum PATI: 0
- maximum PATI: 200

Risk of postoperative complications

- The risk of postoperative complications is low if the PATI is ≤ 25 .
- The rate of postoperative complications increases sharply if the PATI >25 .

Appendix 2: Clavien-Dindo's Classification of Surgical Complications^{11 12}

Grades	Definition
Grade I:	Any deviation from the normal postoperative course without the need for pharmacological treatment or surgical, endoscopic and radiological interventions. Allowed therapeutic regimens are: drugs as antiemetic's, antipyretics, analgesic's, diuretics and electrolytes and physiotherapy. This grade also includes wound infections opened at the bedside.
Grade II:	Requiring pharmacological treatment with drugs other than such allowed for grade I complications. Blood transfusions and total parenteral nutrition are also included.
Grade III:	Requiring surgical, endoscopic or radiological intervention
Grade III-a:	intervention not under general anaesthesia
Grade III-b:	intervention under general anaesthesia
Grade IV:	Life-threatening complication (including CNS complications) ‡ requiring IC/ICU-management
Grade IV-a:	single organ dysfunction (including dialysis)
Grade IV-b:	multi organ dysfunction
Grade V:	Death of a patient
Suffix 'd':	If the patients suffers from a complication at the time of discharge, the suffix "d" (for 'disability') is added to the respective grade of complication. This label indicates the need for a follow-up to fully evaluate the complication.

‡ brain haemorrhage, ischemic stroke, subarachnoidal bleeding, but excluding transient ischemic attacks (TIA);
IC: Intermediate care; ICU: Intensive care unit.

Appendix 3: Surgical Site Infection defined by WHO¹³

- Superficial incisional, affecting the skin and subcutaneous tissue. These infections may be indicated by localized signs such as redness, pain, heat or swelling at the site of the incision or by the drainage of pus.
- Deep incisional, affecting the fascial and muscle layers. These infections may be indicated by the presence of pus or an abscess, fever with tenderness of the wound, or a separation of the edges of the incision exposing the deeper tissues.
- Organ or space infection, which involves any part of the anatomy other than the incision that is opened or manipulated during the surgical procedure, for example joint or peritoneum. These infections may be indicated by the drainage of pus or the formation of an abscess detected by histopathological or radiological examination or during re-operation. Organ infection is not included within the scope of this guideline.

Appendix 4: Case Report Form

Exploratory laparotomy following penetrating abdominal injuries: a cohort study from a referral hospital in Erbil, Kurdistan region in Iraq

Case Report Form

1 November 2017

FINAL version

Case Report Form (CRF), version 171101, protocol: _____

Patient Data

Patient no

1. Time of admission

 / /

day month year

 :

hours minutes

Unknown

2. Age

 in years

Unknown

3. Sex

Male

Female

Unknown

4. Ethnicity

Arabic

Kurdish

Other

Unknown

If other, specify

5. Civilian/Combatant

Civilian

Combatant

Unknown

If combatant

Iraqi

Peshmerga

IS

Unknown

Other

If other, specify

Investigators signature _____

day month year

Validated by and date: _____

Case Report Form (CRF), version 171101, protocol: _____

Injury Data

Patient no

[figure not shown]
6. Time of injury

hours minutes

day month year

Unknown

7. Geographical location where injury occurred

Unknown

Other

If other, specify location where injury occurred

Investigators signature

day month year

Validated by and date: _____

Case Report Form (CRF), version 171101, protocol: _____

Injury Data continued

Patient no

8. War-related injury

Yes

No

Unknown

9. Cause of injury

(If several causes number in same order as question 20 and 21)

Bullet

Shell

Mine

IED

Unknown

Other

If other, specify

10. Mechanism of injury

(If several number in same order as question 20 and 21)

Gunshot

Stab

Blast

Crush

Fragment

Unknown

Burn

Other

Traffic accident

If other, specify

Investigators signature _____

_____/_____/_____
day month year

Validated by and date: _____

Case Report Form (CRF), version 171101, protocol: _____

Prehospital Care Data

Patient no

11. Care prior to admission to EH

(If several number in chronological order)

First aid

Medical

None given

Unknown

Surgery

If surgery, specify procedure done

day month year

of procedure

12. Provider of care prior to EH

(If several number in chronological order)

MSF

Aspen

ICRC

Unknown

Samaritan Purse

None

Department of Health

Other, specify

Investigators signature

day month year

Validated by and date: _____

Case Report Form (CRF), version 171101, protocol: _____

Prehospital Care Data cont.

Patient no

13. Mode of transport to EH

(If several number in chronological order)

Military

Private car

Motorcycle

Ambulance

Unknown

Other, specify

14. Medical history

Healthy

Unknown

Prior surgery

Prior medical

If prior surgery specify procedure(s)

If prior medical condition(s) specify

Investigators signature

_____ / /
day month year

Validated by and date: _____

Case Report Form (CRF), version 171101, protocol: _____

Clinical Data at OPD

Patient no

15. Body temperature

in Celsius.

Unknown

16. Heart rate

in beats/min

Unknown

17. Blood pressure

 /

in mmHg

Systole

Diastole

Unknown

18. Pregnant

Yes

No

Unknown

19. Pregnancy status based on

Lab

Question

Status

Unknown

20. Site and extent of abdominal wound

If >2 injuries
use remarks

Mark each wound by number

1.

Brief description of size and depth

2.

Brief description of size and depth

Investigators signature

_____ / _____ / _____

day month year

[figure not shown]
[figure not shown]
Validated by and date: _____

Case Report Form (CRF), version 171101, protocol: _____

Clinical Data at OPD cont.

Patient no

21. Other injuries

If >3 injuries
use remarks

Mark each wound by number

1.

Brief description of size and depth

2.

Brief description of size and depth

3.

Brief description of size and depth

Investigators signature

_____/_____/_____
day month year

Validated by and date: _____

Case Report Form (CRF), version 171101, protocol: _____

Preoperative Data

Patient no

22. Preoperative haemoglobin

 g/dL

Unknown

23. Preoperative transfusions

None given

Unknown

 Units of whole blood Units of packed red blood cells Units of Platelets Units of Plasma

24. Use of preoperative radiology

No

Unknown

 Computed Tomography (CT)

If CT was used, specify findings

 Conventional radiology (X-ray)

If X-ray was used, specify findings

Investigators signature _____

_____/_____/_____
day month year

Validated by and date: _____

Case Report Form (CRF), version 171101, protocol: _____

Operative Data cont.

Patient no

Procedure done cont.

Colon resection with anastomosis

Yes

No

Unknown

If anastomosis, specify site(s) and technique(s)

Stoma/Bowel deviation

Yes

No

Unknown

If stoma(s), specify site(s) and technique(s)

Vascular repair

Yes

No

Unknown

If vascular repair(s), specify location(s) and technique(s)

Splenectomy

Yes

No

Unknown

Other

Yes

No

Unknown

If other(s), specify location(s) and procedure(s)

29. Perioperative complication

Yes

No

Unknown

If yes, specify type

Investigators signature

_____ / /

day month year

Validated by and date: _____

Case Report Form (CRF), version 171101, protocol: _____

Postoperative Data

Patient no

30. Postoperative antibiotic prophylaxis

(without treating a defined infection)

No

Unknown

Yes

If yes, specify type, doses and duration

31. Postoperative infection

(If several is possible mark all with with appropriate postop. day.)

No

Unknown

